## 10. Statistical Considerations

### 10.1. Sample Size Determination

Approximately 375 study participants will be randomized in a 1:1:1 ratio to LY3209590 in one of two dosing algorithms or insulin degludec treatment arms, assuming a 20% dropout rate resulting in approximately 300 total completers at 32 weeks (100 completers per treatment arm). The sample size was calculated based on the statistical power for the primary and liver safety endpoints.

- The 300 completers will provide 90% statistical power to demonstrate the noninferiority of the pooled LY3209590 arms versus insulin degludec for the change in HbA1c from baseline to 32 weeks (assuming non-inferiority margin is 0.4%, the SD is 1.1% and true mean difference is 0%) using two sided t-test at  $\alpha = 0.1$ .

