4.1. General Considerations

All data will be entered, verified, and archived at a contract research organization (CRO) external to Eli Lilly and Company (Lilly) and/or at Lilly. Data listings, summaries, and analyses will be performed by a CRO and/or by Lilly under the guidance and approval of statisticians at Lilly.

Statistical analysis of this study will be the responsibility of Lilly. Any change to the data analysis methods described in the protocol will require an amendment ONLY if it changes a principal feature of the protocol. Any other change to the data analysis methods described in the protocol, and the justification for making the change, will be described in this SAP and/or in the clinical study report (CSR). Additional exploratory analyses will be conducted, as deemed appropriate.

Unless otherwise specified, listings will be ordered by the patient ID nested within the investigator site.

The patient populations used for this study are described below:

Population and Analysis Set	Description
Entered/Enrolled Population	All study participants who sign informed consent
Randomized Population	All study participants who are randomly assigned a treatment arm
Efficacy analysis set (EAS)	Data for all randomized study participants who receive at least one dose of study medication, excluding data after using rescue medication(not acute therapy) or stopping study medication (last dose date + 10 days). In the event of a treatment error, participants will be analyzed according to the treatment they actually received.
Safety Population	All randomized study participants who receive at least one dose of study medication.
CGM Population	All randomized study participants who receive at least 1 dose of study medication, and have CGM data from at least 1 collection period.

Abbreviations: CGM = continuous glucose monitoring.

Safety analyses will be conducted using the Safety Population with all data collected during the study including treatment and follow-up period regardless of the treatment disposition status. Efficacy analyses will be conducted on the efficacy analysis set (EAS), unless otherwise specified.

Unless otherwise noted, all tests of treatment effects will be conducted at a 2-sided alpha level of 0.10 and confidence intervals (CIs) will be calculated at 90%, 2-sided. All tests of interactions between treatment groups and other factors will be conducted at a 2-sided alpha level of 0.10.

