4.7. Primary Outcome and Methodology

The primary efficacy measure of change in HbA1c at Week 32 (together with HbA1c measure at other postbaseline visits) will be summarized and analyzed using an MMRM approach on the EAS. This model implicitly adjusts for missing data through a variance-covariance structure. This model will include the fixed effects of treatment (LY3209590 Algorithm 1, LY3209590 Algorithm 2, insulin degludec), stratification factors (country, BMI strata [BMI <30 or ≥30], sulfonylureas use[Y/N]), visit, treatment by visit interaction, and baseline value of the dependent variable as the fixed effects. The HbA1c is reported in unit of % and will be converted to the unit of mmol/mol using the following formula: HbA1c in mmol/mol = 10.93*HbA1c in % - 23.5 (<http://www.ngsp.org/ifccngsp.asp>). HbA1c analysis will be conducted based on both units.

In the MMRM model, the within-patient errors are modeled as an unstructured variance-covariance matrix. If the analysis fails to converge, the following variance-covariance matrix will be used (in order) until one converges:

1. toeplitz with heterogeneity
2. autoregressive with heterogeneity
3. compound symmetry with heterogeneous variances
4. toeplitz
5. autoregressive
6. compound symmetry without heterogeneous variances

The Kenward-Roger approximation will be used to estimate denominator degrees of freedom for the MMRM models. The following is an example SAS code:

```
proc mixed data=DATA;
  class TREATMENT STRATIFICATIONS VISIT PATIENT;
  model HbA1c=BASELINE TREATMENT STRATIFICATIONS VISIT
        VISIT*TREATMENT / solution ddfm=kr;
  repeated VISIT / subject=PATIENT type=un;
  lsmeans TREATMENT*VISIT/ pdiff cl alpha=0.1 om=DATA;
run;
```

The 2-sided 90% CI for the LS mean for the individual treatment arms, treatment LS mean difference (LY3209590 Algorithm 1 vs. insulin degludec, LY3209590 Algorithm 2 vs insulin degludec, and LY3209590 Algorithm 1 vs LY3209590 Algorithm 2) in the change in HbA1c at 32 weeks will be constructed. Similar summary will be provided for the comparison between pooled LY arm and insulin degludec based on the contrast from the above MMRM model.

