4.10.3.2. Hypoglycemia Events

Both the rate per 1 patient year and incidence of the following type of hypoglycemia events will be derived and analyzed: documented hypoglycemia, documented nocturnal hypoglycemia (occurs between bedtime and waking), and documented non-nocturnal hypoglycemia (occurs between waking and bedtime).

[Table BDCM.1](#) provides the summary of statistical method for hypoglycemia event related analysis. Additionally, severe hypoglycemia events will be listed, and incidence of severe hypoglycemia will be compared between treatments using Fishers' exact test.

Table BDCM.1. Hypoglycemia Event Related Analyses

Endpoint	Time Point*	Statistical Method
Rate of hypoglycemia events defined by glucose <54 mg/dL (3.0 mmol/L) and ≤ 70 mg/dL (3.9 mmol/L) 
 • Documented • Nocturnal • Non-Nocturnal 	0-12, 0-32, 12-32 weeks, post-treatment period (up to Visit 801)*	Negative binomial regression with treatment, baseline SU use (yes/no), baseline HbA1c, baseline hypoglycemia event rate with the same category of the dependent variable, log (exposure in year) as the offset in the model.
Incidence of hypoglycemia events defined by glucose <54 mg/dL (3.0 mmol/L) and ≤ 70 mg/dL (3.9 mmol/L) 
 • Documented • Nocturnal • Non-Nocturnal 	0-12, 0-32, 12-32 weeks, post-treatment period (up to Visit 801)*	Logistic regression with treatment, baseline SU use (yes/no), baseline HbA1c, baseline hypoglycemia event rate with the same category of the dependent variable in the model. Note that the logistic regression will be conducted when ≥10 patients with this event.

 • Proportion of patients with HbA1c <7% without nocturnal hypoglycemia event • Proportion of patients with HbA1c ≤6.5% without nocturnal hypoglycemia event 	0-32 weeks	Logistic regression with treatment, baseline SU/meglitinide use (yes/no), baseline HbA1c, and baseline nocturnal hypoglycemia event rate in the model.

Abbreviations: HbA1c = hemoglobin A1c.

Note: The hypoglycemia rate per year during defined period is calculated by the number of hypoglycemia within the period/number of days patient at risk within the period*365.25 days. The hypoglycemia incidence during defined period indicates if the patient has at least 1 hypoglycemia events within the period (Yes/No). The baseline hypoglycemia rate is the rate calculated between Visit 1 and Visit 3.

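### The hypoglycemia incidence models run once 10 patients have an event, with no per-arm condition, so an arm with zero events leaves its odds ratios non-finite; the risk is confined to sparse cells.

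*SAP*

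**What the plan says.** SAP Section 4.10.3.2, Table BDCM.1, gives the incidence model as "Logistic regression with treatment, baseline SU use (yes/no), baseline HbA1c, baseline hypoglycemia event rate with the same category of the dependent variable in the model". The table then adds: "Note that the logistic regression will be conducted when ≥10 patients with this event". It does not say whether the 10 are counted over all arms or within each; the total is the plain reading. It sets no minimum per arm, names no penalised or exact logistic method, and gives no rule for an empty arm or for a total below 10.

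The row covers three categories (documented, nocturnal, non-nocturnal), two glucose cut-offs (<54 and ≤70 mg/dL) and four periods: "0-12, 0-32, 12-32 weeks, post-treatment period (up to Visit 801").

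Severe hypoglycemia is handled apart: "incidence of severe hypoglycemia will be compared between treatments using" Fisher's exact test. SAP Section 4.1 also names Fisher's exact test for categorical measures in general, but does not link it to this model as a fallback. The general significance rule there is that "all tests of treatment effects will be conducted at a 2-sided alpha level of 0.10".

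**The concern.** A total count of 10 does not protect a three-arm comparison. All 10 events can fall in two arms. Maximum likelihood then has no finite solution for the empty arm, and software reports a very large coefficient with a far larger standard error, or a separation warning. An odds ratio and 90% interval cannot be reported for the contrast that shows the largest imbalance in the data.

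Protocol Section 7.8.2.2 states that the effect of LY3209590 on hypoglycemia is unknown and that assessing the risk is a study objective. SAP Section 3.2.2 makes documented and documented nocturnal incidence secondary safety outcomes. A rule that can return no usable estimate in a sparse cell is therefore worth correcting before results are known.

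**Working it through.** **Inputs.**
- Allocation, Protocol Section 10.1: "Approximately 375 study participants will be randomized in a 1:1:1 ratio to LY3209590 in one of two dosing algorithms or insulin degludec treatment arms", so 125 per arm and 250 LY patients pooled.
- Treatment levels, SAP Section 4.7: "treatment (LY3209590 Algorithm 1, LY3209590 Algorithm 2, insulin degludec"). This is stated for the primary model and is assumed to apply here too.
- Expected hypoglycemia incidence: not given in the documents. Ranges are assumed below.

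**1. The plan's own figure.** The documents give no figure for the logistic rule, so only the sample size can be reproduced. With 200 LY and 100 degludec completers, SE = 1.1 × √(1/200 + 1/100) = 0.135. Power = Φ(0.4/0.135 − 1.645) ≈ 0.907, against the stated 90%. Then 300/(1 − 0.20) = 375. Both agree.

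**2. Model size and scope.** Slopes: 2 + 1 + 1 + 1 = 5, so 10/5 = 2 events per slope at the trigger. Models: 3 categories × 2 cut-offs × 4 periods = 24. Secondary at most: 2 categories × 2 cut-offs × 3 treatment-period windows = 12. SAP Section 3.3 lists non-nocturnal events as exploratory, and Protocol Section 4 lists follow-up hypoglycemia as exploratory.

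**3. What an empty arm does.** That arm contributes only factors (1 − p) to the likelihood, which keep rising as its log-odds go to −∞, so no maximum exists. The fits below use one simulated dataset per split (assumed: SU 30%, HbA1c mean 8.1 and SD 0.9, baseline event count Poisson with mean 0.3). Each cell gives LY Algorithm 1, then Algorithm 2, versus degludec. The Firth intervals shown are Wald-type.

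| Events: degludec/LY1/LY2 | Maximum likelihood OR (90% CI) | Firth OR (90% CI) | Fisher p, pooled LY vs degludec |
|---|---|---|---|
| 0/5/5 | not finite; not finite | 13.3 (1.3–135); 12.0 (1.2–123) | 0.035 |
| 1/4/5 | 4.8 (0.75–31); 5.2 (0.84–32) | 3.6 (0.79–16); 3.8 (0.87–16) | 0.17 |
| 0/10/10 | not finite; not finite | 23 (2.3–237); 24 (2.4–247) | 0.0003 |
| 1/10/9 | 11.1 (1.9–63); 9.8 (1.7–57) | 7.7 (1.9–32); 6.8 (1.6–28) | 0.006 |
| 5/5/0 | 1.07 (0.37–3.1); not finite | 1.07 (0.4–2.8); 0.09 (0.01–0.9) | 0.31 |

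For 0/5/5 the first log odds ratio moves from 6.1 (SE 8.7) at 8 iterations to 13.1 (SE 286) at 15. The Wald statistic is then 13.1/286 = 0.046, on data where Fisher's test gives 0.035.

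**4. How often, given the total.** At OR 1, P(no degludec events | T) = C(250,T)/C(375,T). At other odds ratios it follows Fisher's noncentral hypergeometric distribution.

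| T | OR 1 | OR 2 | OR 3 | OR 5 | OR 10 |
|---|---|---|---|---|---|
| 10 | 1.6% | 10% | 21% | 37% | 60% |
| 15 | 0.2% | 3.1% | 9.0% | 22% | 46% |
| 20 | 0.02% | 0.9% | 3.8% | 13% | 35% |

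Counting any of the three arms at OR 1, the chance is 4.9% for T = 10 and 0.6% for T = 15. Simulations over 10 to 15 total events, with assumed covariates, gave an empty arm in 1.5% to 2.5% of datasets at OR 1, about 6% at OR 2 and 19% to 21% at OR 4.

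**5. How often, by assumed incidence.**

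| Degludec / LY incidence | P(T ≥ 10) | P(no degludec events given T ≥ 10) |
|---|---|---|
| 1% / 3% | 38% | 17% |
| 1% / 5% | 88% | 26% |
| 2% / 6% | 98% | 7.6% |
| 3% / 9% | about 100% | 2.2% |
| 5% / 15% | about 100% | 0.2% |
| 10% / 10% or more | about 100% | below 0.01% |

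**6. Accuracy when no arm is empty.** Root mean squared error of the log odds ratio, Firth against maximum likelihood, with 10 to 15 events: 0.65 against 0.76 at OR 1, 0.67 against 0.80 at OR 2, 0.70 against 0.73 at OR 4. Firth was lower at all three.

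**The case against.** A reader might infer that the model breaks whenever events fall mainly in the LY arms, exactly where there is a signal. The calculations do not support that. One degludec event is enough for a finite estimate: the 1/10/9 split gives odds ratios whose intervals exclude 1. An empty LY arm fails in the same way (5/5/0), so the failure is not tied to harm from LY. What holds is that an empty degludec arm becomes more likely as the LY excess grows.

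A reader might also infer that the nocturnal <54 mg/dL and post-treatment cells are likely to sit near the trigger. The documents give no incidence to support this. Participants wear real-time CGM and record hypoglycemia-related readings (Protocol Section 9.4.4), so low counts cannot be presumed. Protocol Section 9.2.2.1 introduces the <54 mg/dL definition for additional analysis, and the rarest secondary event, severe hypoglycemia, already has an exact test.

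It can further be said that an imbalance would not go unseen. Counts would show it, and a likelihood-ratio test of treatment still works under separation (p = 0.011 for 0/5/5, 0.0002 for 0/10/10). This is fair, but the SAP does not specify that test for this model, and it supplies no odds ratio or interval. The negative binomial rate model cannot stand in either, because its log rate ratio also diverges when an arm is empty.

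The objections on scope stand and keep the point minor. They do not remove the missing rule.

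**Conclusion.** The concern holds as a narrow one. The trigger is a stated rule that, followed as written, can return non-finite treatment odds ratios. This needs at least one arm with zero events. Given 10 to 15 events in total, that is about 2%, 6% and 20% of datasets at odds ratios of 1, 2 and 4. With events in every arm, the treatment estimate is normally finite but imprecise.

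The figures assume 125 patients per arm, three treatment levels in the model, 10 read as a total, and assumed covariates and incidences. The statement that the risk is negligible at a degludec incidence of about 5% or more assumes LY incidence is no lower; a rare-event LY arm could still be empty. At most 12 of 24 models are secondary and severe events are unaffected, so this is a desirable correction and does not threaten the trial's main conclusions.

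**What to change.** In Table BDCM.1, fit the incidence models by Firth penalised likelihood with profile-likelihood 90% confidence intervals (PROC LOGISTIC, FIRTH option), at least whenever any arm has few or zero events. State that the count of 10 is a total. Report Fisher's exact test, as already planned for severe events, when an arm has zero events or the total is below 10; the second condition also closes the gap below the trigger.

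The cost is one procedure option and one or two sentences. Firth shrinks estimates slightly toward the null in sparse cells, and the effect is negligible when events are many. Intervals in empty-arm cells will be finite but wide, as the 0/5/5 example shows. The change does not cover the negative binomial rate models, so the SAP should also say what is reported there when an arm is empty.

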### **7.8. Treatment After the End of the Study**

#### **7.8.1. Treatment After Study Completion**

Investigational Product will not be made available to study participants after conclusion of the study

Beginning on the evening of the last treatment visit (Visit 21 [Week 32] or ET visit), study participants will resume their previous basal insulin therapy. As washout of LY may take up to 10 weeks to complete, previous basal insulin therapy will be instituted using the Riddle algorithm as need based on FBG (Section 7.2.1.2.). For example, no insulin would be required until the study participant's blood glucose increases to >100 mg/dL, and then daily basal insulin would be initiated and adjusted based on weekly algorithm FBG.

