### 10.2. Analysis Sets

For purposes of analysis, the following populations and analysis sets are defined:

Population and Analysis Set	Description
Enrolled	All study participants who sign informed consent
All randomized study participants	All study participants who are randomly assigned a treatment arm
Efficacy analysis set (EAS)	Data for all randomized study participants who received at least one dose of study medication, excluding data after using rescue medication or stopping study medication (last dose date + xx days). In the event of a treatment error, participants will be analyzed according to the treatment they actually received.
Full analysis set (FAS)	Data for all randomized study participants, regardless of titration, stop of study medication, or rescue.

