3.2.2. Safety

To compare the safety of LY3209590 versus insulin Degludec treatment groups for the following:

1. Documented, documented nocturnal and severe hypoglycemia incidence and rates during the treatment period (0-12, 12-32, and 0-32 weeks);
2. Treatment-emergent serious adverse events (SAEs) incidences;
3. Body weight change from baseline at Week 12 and 32.

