4.10.1. Study Drug Exposure

Exposure in days in the study will be calculated for each patient and summarized by treatment group. The mean of exposure will be compared between treatment groups using 2-sample *t*-test. Exposure during the treatment period will be calculated from date of first study basal insulin dose collected in the electronic case report form [eCRF] to date of discontinuation from study treatment (i.e., the last dose date for insulin degludec, and last dose date + 7 days for LY3209590 to account for the weekly injection). The sum of exposure in total patient years will also be provided.

Frequency of subjects falling into the following different exposure ranges will also be summarized: >0 days, ≥ 7 days, ≥ 14 days, ≥ 30 days (1 month), ≥ 60 days (2 months), ≥ 90 days (3 months), ≥ 120 days (4 months), ≥ 183 days (6 months) days.

In addition, the duration of follow-up in days for each individual patient is calculated from the date of last dose of study drug for insulin degludec/last dose of study drug + 7 days for LY3209590 to the last study visit date. The duration of the follow-up in days will be summarized (n, mean, standard deviation, median, sum in total patient years, minimum and maximum) by treatment group.

The duration on study from date of first study drug to the last study visit date (including the follow-up visit) will also be summarized by treatment group, the following summary statistics will be provided: n, mean, standard deviation, median, sum in total patient years, minimum and maximum.

A by-patient listing of drug exposure data will be created to provide data for the CSR appendix of Compliance and/or Drug Concentration Data.

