*Analyses for endpoint during post-treatment period (up to Visit 801) will include all of the data after study drug discontinued on Safety population; analyses for endpoints during other time points will include all data before study drug discontinued on Safety population.

The following is the example of the SAS code of the negative binomial regression for analyzing the rate of hypoglycemia events.

```
proc glimmix empirical data=DATA;
class TREATMENT;
model HYPO_FREQ=TREATMENT [BASELINE_HYPO_RATE]
/dist=nb link=log offset=log(exposure in
days/365.25);
lsmeans TREATMENT/OM pdiff cl alpha=0.1 ilink;
random _residual_;
run;
```

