4.11. Continuous Glucose Monitoring Analysis

4.11.1. General Consideration

The continuous glucose monitoring system will be offered to all patients at selected sites in Study I8H-MC-BDCM. Interstitial glucose (ISIG) values will be collected by the CGM at 5-minute intervals. Continuous glucose monitoring recordings will be obtained for all patients throughout the treatment phase of the study. The device readings and alarms will not be blinded to the patients so that they can be warned of hypoglycemia and appropriately manage any hypoglycemic episodes.

All patients who are randomized to 1 of the study treatments (LY3209590 Algorithm 1, LY3209590 Algorithm 2, insulin degludec) receive at least 1 dose of study treatment, and have CGM data from at least 1 collection period which will be included in the analyses. The data collected after permanent discontinuation of investigational product will be censored. There will be no multiplicity adjustment. Since the sensor takes about 2 hours to reach the steady state after insertion, it is recommended to only use the steady state data for analysis.

Summary statistics will include the number of observations, mean, median, maximum, minimum, and SD for all continuous measures. For categorical measures, the number of observations, proportion, and frequencies will be included in summary statistics. All analyses will be performed for data collected by visit and treatment.

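### The note to SAP Table BDCM.1 drops hypoglycemia after an early stop from the 0-12, 12-32 and 0-32 week analyses, against the protocol's all-data rule for safety

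*SAP*

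**What the plan says.** The secondary safety objective in SAP 3.2.2 is "Documented, documented nocturnal and severe hypoglycemia incidence and rates during the treatment period (0-12, 12-32, and 0-32 weeks"). SAP Table BDCM.1 (section 4.10.3.2) analyses documented, nocturnal and non-nocturnal events at two glucose thresholds in those three windows and in a post-treatment window. Rates use negative binomial regression with log exposure as offset. Incidence uses logistic regression with no exposure term.

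The note to the table splits the data at drug discontinuation. For the three week-based windows, "analyses for endpoints during other time points will include all data before study drug discontinued on Safety population". For the rest, "Analyses for endpoint during post-treatment period (up to Visit 801) will include all of the data after study drug discontinued on Safety population". The note gives no date for discontinuation.

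Other places set a different rule:

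- SAP 4.1 bases safety analyses on "all data collected during the study including treatment and follow-up period regardless of the treatment disposition status". SAP 4.10 likewise includes measurements made after the drug is stopped.
- The protocol synopsis and Protocol 10.3.4 use the full analysis set (FAS) for safety. Protocol 10.2 defines it as "Data for all randomized study participants, regardless of titration, stop of study medication, or rescue".

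Three further statements bear on the point. Protocol 7.8.1 says "As washout of LY may take up to 10 weeks to complete". SAP 4.10.1 ends exposure at the last dose for degludec and at "last dose date + 7 days for LY3209590 to account for the weekly injection". For continuous glucose monitoring (CGM), SAP 4.11.1 says "The data collected after permanent discontinuation of investigational product will be censored".

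**The concern.** Protocol 3.2 names more frequent or longer hypoglycemia as the possible drawback of so long-acting an agent. The weeks after an early stop are part of where that would show. Protocol 5.1.1 encourages early stoppers to stay in the study, and Protocol 9.2.2.1 collects hypoglycemia until the last visit, so the data are meant to exist.

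Stopping can also depend on the outcome: Protocol 7.8.2.2 lists discontinuation of study drug among the responses to continuing hypoglycemia. A participant can therefore leave the window because of the event being measured.

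Take an LY participant who stops at Week 8 and has a first event in Week 10. The event is under residual drug and inside Weeks 0-32, but the participant enters the 0-32 week logistic model as event-free. The event appears only in the post-treatment row, alongside completers who have gone back to their own insulin. At the planned 20% dropout, completers are 100 of 125 per arm.

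**Working it through.** **The plan's own figures.** The plan gives none for hypoglycemia. Its only power statement is 90% for HbA1c, pooled LY against degludec. It reproduces: 0.4 / (1.1 × √(1/200 + 1/100)) = 2.97, and 2.97 − 1.645 = 1.32, which is 90.7%. Nothing below depends on it.

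**Inputs.**
- 375/3 = 125 per arm over 32 weeks, so 4,000 patient-weeks (Protocol 10.1).
- Share stopping early: not given. The planned 20% dropout is the upper value; 10% and 5% are also shown. Stoppers are assumed to stay under observation.
- Time of last dose S: assumed uniform over Weeks 0-32.
- Residual window W: 10 weeks (Protocol 7.8.1, stated as a maximum). The low case is 4 weeks, borrowed as an assumption from the 4 to 10 weeks to steady-state glucose in Protocol 5.5. The half-life is redacted. The contraception criterion implies (15 × 7 − 90)/3 = 5 days, which fits the shorter window better, so the two passages need reconciling.
- Data cut: at the last dose, or 7 days later if SAP 4.10.1 applies.

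**Time left out, 20% stopping (25 people), W = 10.**
- Cut at last dose: the mean of min(10, 32 − S) is (22 × 10 + 10 × 5)/32 = 8.44 weeks per stopper. Total time lost is 25 × 16 = 400 patient-weeks, which leaves 3,600 counted. Residual-LY time lost is 25 × 8.44 = 211, and 211/3,600 = 5.9%.
- Cut 7 days later: (22 × 9 + 9 × 4.5)/32 = 7.45 weeks per stopper. Total time lost is 25 × 31²/(2 × 32) = 375, which leaves 3,625 counted. Residual-LY time lost is 25 × 7.45 = 186, and 186/3,625 = 5.1%.

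Residual-LY time omitted, as a share of counted LY time (cut at last dose / 7 days later):

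| Stop share | W = 10 weeks | W = 4 weeks |
|---|---|---|
| 20% | 5.9% / 5.1% | 2.6% / 1.9% |
| 10% | 2.8% / 2.4% | 1.2% / 0.9% |
| 5% | 1.4% / 1.2% | 0.6% / 0.4% |

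**Shorter follow-up.** Suppose stoppers are seen only to Visit 803, about 6 weeks after the last dose. With S uniform over Weeks 0-31 and the 7-day cut, the omitted time is (26 × 5 + 5 × 2.5)/31 = 4.60 weeks per stopper. Multiplied by 0.20 this is 0.92 week per LY participant, or 2.9% of 32 weeks. With the full 10 weeks it is (22 × 9 + 9 × 4.5)/31 = 7.69 weeks, then 1.54 weeks, or 4.8%.

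**Incidence.** Assume a constant rate λ, so P(any event by week t) = 1 − exp(−λt/52.18), with events cut at the last dose. The documents give no rate; these values are illustrative.

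| λ per year, stop share | On-drug rule | Plus 10-week window | All data to Week 32 |
|---|---|---|---|
| 1, 20% | 41.7% | 44.0% | 45.8% |
| 1, 10% | 43.8% | 44.9% | 45.8% |
| 3, 20% | 78.1% | 81.9% | 84.1% |

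The change goes one way, because adding follow-up time cannot remove a first event.

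**Rate.** Let the rate in the residual window be r times the on-drug rate (20% stopping, W = 10, cut at last dose). The rate with the window included, relative to the rate without it, is (3,600 + 211r)/(3,600 + 211). This is 0.972 at r = 0.5, 1.000 at r = 1 and 1.055 at r = 2. The sign depends on r, which is unknown.

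**Mismatch of dates.** LY completers take their last dose at Week 31. If events were cut there while the exposure offset ran 7 days longer, a completer's rate at a constant hazard would be 31/32 = 0.969 of the true value, 3.1% too low. The note does not rule this out.

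**The case against.** The best defence is that nothing leaves the report. The post-treatment row uses the same models, thresholds and arms, and the two windows together cover all the data. SAP 4.10's statement that post-drug data are included is then met across the pair. The synopsis and SAP 3.2.2 tie the endpoint to the treatment period. Protocol Table BDCM.2 lists treatment plus follow-up separately as exploratory, and Protocol 10.3.4.3 leaves the details to the SAP. Events after a stop also reflect whatever glucose-lowering therapy came next.

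Much of this stands. An on-drug analysis is legitimate and should be kept. But the windows are labelled by study week, and the protocol's safety set disregards drug status. Leaving methods to the SAP does not change that set. Protocol 10.3.1 asks for changes to be justified in the SAP or study report, and the SAP offers no reason for this one. The pooled post-treatment row cannot show early stoppers' residual-drug weeks.

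A reader might go further in three ways that the documents do not support:

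- *That the rule biases the comparison in favour of LY.* The direction for the rate depends on the unknown post-stop rate. Cutting observation short also lowers incidence in the degludec arm, by an amount that depends on its own stops. If the SAP 4.10.1 dates apply, LY gains 7 counted days that degludec does not.
- *That the whole secondary safety endpoint is affected.* Severe hypoglycemia is handled outside the table and its note, with no stated window, so the general all-data rules keep those events. They are also reported as serious adverse events. CGM hypoglycemia is exploratory (SAP 3.3).
- *That completers' follow-up CGM is certainly censored.* SAP 4.11.1 speaks of permanent discontinuation, a term Protocol 8.1.1 uses for early stopping. Applying it to completers is inference.

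**Conclusion.** The contradiction is in the text and does not depend on any assumption: the note restricts three week-based safety windows that the protocol and the SAP's own general rules leave unrestricted. For documented, nocturnal and non-nocturnal hypoglycemia, the loss of incidence in an arm with early stops can only be downward.

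The size is modest. Across the assumed range, omitted residual-LY time runs from about 0.5% to 6% of counted LY time. The top of the range needs 20% early stops, full observation afterwards and drug action for all 10 weeks, so it is an upper case and not an estimate. In the incidence illustration at 20% stops, the on-drug rule lowers LY incidence by about 2 to 4 percentage points against adding the 10-week window, and by about 4 to 6 against full follow-up to Week 32. That rests on invented event rates. The use of the 7-day date from SAP 4.10.1 for the event cut-off is also an inference.

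The point is worth correcting because the trial's own safety question concerns prolonged action and the correction is cheap. It does not show that the planned comparison favours either arm.

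**What to change.** 1. In the note to SAP Table BDCM.1, base the 0-12, 12-32 and 0-32 week rates and incidences on all events to the end of the interval or of participation, whatever the study drug status. Use days observed as the rate offset. Report the present on-drug version alongside as supportive.
2. State the discontinuation date for each arm, and use the same date for events and for the offset in the on-drug version.
3. In the post-treatment row, show early stoppers separately from completers.
4. State the data window for severe hypoglycemia.
5. In SAP 4.11.1, add a by-arm summary of the CGM hypoglycemia data available after discontinuation and in follow-up. SAP 4.11.2 reports lost recordings when visits are more than 4 weeks apart. The on-site visits at Weeks 32 and 37, and Visits 802 and 803, are each about 5 weeks apart, so coverage should be reported too.

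The cost is SAP wording, a second run of the same models and a few extra tables; no new data are collected. The drawback is that events after a stop partly reflect other glucose-lowering therapy, which is why both versions should be shown.
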